7.6.1 Survey administration procedures

In order to maintain confidentiality, the survey should be conducted in an area away from other people, where the participant will feel comfortable discussing personal information with the research staff. The survey should last about 30 minutes and should be completed in one sitting; make sure the participant is aware of the duration of the survey before beginning. It is the research staff’s responsibility to obtain full and accurate information from participants.

Strategies for starting baseline survey with a new participant:

- Emphasize the time commitment required to complete survey (approximately 30 minutes)
- Get a verbal commitment from the participant that they are able and willing to stay for the entire survey
- Only begin survey with participant who can commit to completing the survey now

Strategies and procedures for successfully administering the survey include:

- Read clearly and in a natural rhythm and tone; read as if you were speaking.
- If the answer provided seems inappropriate for the question asked, kindly acknowledge the response and then repeat the question, clarifying where needed.
- Each question must be asked of each participant in the same way and in the same order to ensure that comparable information is being obtained from all the participants in the study.
- Transition sentences appear throughout the survey to help you introduce a new topic. Read these out loud and in full as they often contain information for the participant on how to answer the following set of questions.
- “Don’t read out loud” will often appear in multiple choice questions for the answers “don’t know or refused”. Study participants may not know the answer to a question and are allowed to refuse to answer any question, but don’t read this aloud as an option; let the participant tell you.

See **section 12.3.1** for instruction on using CASIC.

7.6.2 Completing surveys when participant needs to leave

At times, a participant may need to leave before administration of a survey is complete. If the participant completed approximately less than half the survey, staff should inform the participant that they will need to restart the survey and complete it at a future date.

Instructions for when a client does not start a survey or completes less than half:

- If possible, schedule a day and time to complete the survey within the next two weeks
- Verify the participant's contact information, and the information for their additional contacts (participant, friend, family member) in order to place reminder calls
- Remind client of the program benefits / incentive available once survey is completed
- Save participant ID# used to enter baseline data into ACCESS database and to start CASIC survey
 - Do NOT open the randomization envelope; do NOT assign client to a study group
- In the event the participant does not start or complete the survey within the two week period:
 - The client will be considered lost to follow-up; add note to ACCESS
 - Notify [name] that client did not start/complete survey and was not randomized
 - Do not reuse the participant ID# and destroy the randomization envelope
 - If the participant was completing a follow-up survey, notify [name] that the survey was not completed within the two-week window

Instructions for when a participant completes approximately half of the survey or more:

- Site staff can save the survey and attempt to finish the remainder with the client within two weeks
- If completing a baseline survey, open the randomization envelope with the participant for group assignment before the participant leaves the site
 - If randomized to the intervention group, provide participant with resources and first food package per study protocols
 - If randomized to the control group, provide participant with 1st incentive (\$15 gift card) and have participant sign for receipt of the gift card
- If completing a follow-up survey, provide participant with the correct incentive and have participant sign for receipt of the gift card
- Verify the participant's contact information, and the information for their additional contacts (participant, friend, family member) in order to place reminder calls
- If possible, schedule a day and time to complete the survey within the next two weeks, either in person or over the phone
- Conduct reminder calls to participant and contacts throughout this two week period to ensure they are able to complete survey at next visit (or over the phone)
- If, after two weeks the survey has not been completed, enter a note in ACCESS that the survey was "incomplete"
- Notify [name] that participant will not complete survey

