- **Randomization Plan:** We will use a 6-block randomization scheme to ensure that the rolling enrollment process across multiple food bank sites will distribute participants equally into each study arm over time. This scheme will be generated using the website www.randomization.com for each food bank site separately, which will create a list of the order of randomization by sequential participant ID.
- **Process Responsibilities:** UCSF will be in charge of creating the randomization scheme for each site. This will include generating the randomization list, preparing sealed envelopes by participant ID, and mailing them to each site to open as recruitment progresses. In the event a participant ID is not used (e.g., a client withdraws consent upon learning what group he/she is randomized to), site study staff should note the participant ID number, destroy the number and envelope, and report the event and ID number to UCSF. UCSF staff will determine if any adjustments need to be made to maintain balance between assignments to intervention and control groups, and will instruct study staff accordingly.

Participant Identification Numbers by Study Site	
Site	ID Numbers
Houston	101-399
Detroit	401-699
Oakland	701-999

- **Procedure for Randomizing a Participant:** The research assistant at each food bank will enroll participants into the study. No staff member will know the randomly selected allocation of the participant until the HbA1c screening, informed consent process, and baseline survey is completed. At the conclusion of this baseline visit, the staff member will open the sealed envelope that corresponds to the participant ID number of the enrolled client and determine the arm assignment, either immediate intervention or waitlist intervention.
- **Best Practices for Using Randomization Envelopes:** Study staff that participate in enrollment activities should use the following best practices to ensure consistency in the randomization process, and to foster a satisfactory client experience.
 - Have all of your enrollment materials available when you are meeting with a new participant (e.g., consent forms, education materials, survey materials, and randomization envelopes)
 - It is especially important to have the participant’s randomization envelope at your table (and in plain sight) during the entire enrollment process
 - Have only 1 randomization envelope at the table for each participant

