12.3.2 CASIC Instructions

CASIC data collection software will be used to record all data from participant baseline and follow-up surveys. CASIC is a secure web-based data collection software hosted on servers at UCSF. To access CASIC via the internet, go to <https://faithdm.ucsf.edu/CASIC/> and sign in using your secure log-in credentials. When internet access is not reliably available, site laptops will be equipped with CASIC Remote. Instructions on how to use CASIC and CASIC Remote follow.

Note: because CASIC is accessible in both online and offline formats for use in completing participant surveys, we will never use paper versions of the participant surveys. Using CASIC exclusively for survey completion will help to maintain consistent, quality data collection, and reduce potential survey administration problems inherent with the use of paper surveys (e.g., correct implementation of the complex skip patterns used throughout the surveys).

Instructions for using CASIC

1. Go to <https://faithdm.ucsf.edu/CASIC/> and log-in
2. Select “FAITH-DM” study
3. From the drop-down menu, select the assessment you wish to administer, the food bank from which the participant was recruited, and the participant ID (from randomization envelop)
4. Begin assessment, being sure to double check accuracy of all information entered
5. Whenever possible, complete survey in single session

Instructions for using CASIC Remote

1. Open CASIC remote from the desktop while internet connection is still available and select “sync” in order to ensure use of the most up-to-date survey (see **section 12.3.2**)
2. In the field, open CASIC remote, log in, and select “Start Assessment”
3. From the drop-down menu, select the assessment you wish to administer, the food bank from which the participant was recruited, and the participant ID
4. Begin assessment, being sure to double check accuracy of all information entered
5. Whenever possible, complete survey in single session
6. When internet connection is reestablished at the end of each day during which data collection took place, click “sync” again to upload all data to the server

For more detailed information regarding CASIC, visit www.westportal.com.

All survey data should be correctly entered into CASIC within **14 days** from survey initiation. Contact UCSF Project Coordinator ([name]) with any CASIC-related questions or issues.

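### Holding a sealed, ID-numbered envelope for up to two weeks can let unblinded staff deduce a not-yet-randomised client's arm before that client is brought back

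*Combined protocol and SAP*

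**What the plan says.** Section 8 sets the scheme: "We will use a 6-block randomization scheme". It is generated separately for each food bank, "which will create a list of the order of randomization by sequential participant ID". UCSF prepares sealed envelopes labelled by participant ID and mails them to the sites, where staff open each one at enrolment. Section 12.3.2 has staff start the online survey by selecting "the participant ID (from randomization envelop"). The ID and the randomisation slot are therefore the same thing, and the slot is taken up before the survey begins.

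Section 7.6.2 covers a client who has to leave. If the survey was not started, or less than about half was done, the instruction is: "Save participant ID# used to enter baseline data into ACCESS database and to start CASIC survey". Staff are also told: "Do NOT open the randomization envelope; do NOT assign client to a study group". They are then told: "If possible, schedule a day and time to complete the survey within the next two weeks". If two weeks pass without completion, the client is classed as lost to follow-up, a note goes into Access, the coordinating team is told that the client was not randomised, and the instruction is: "Do not reuse the participant ID# and destroy the randomization envelope". If about half or more was done, the envelope is opened before the client leaves.

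Section 8 gives this assurance: "No staff member will know the randomly selected allocation of the participant until the HbA1c screening, informed consent process, and baseline survey is completed". Section 6 says that the study is not blinded.

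**The concern.** Concealment has to last until a person is irrevocably in the trial. Here a slot is set aside, still sealed, while enrolment continues around it. Nothing in the documents pauses enrolment or re-sequences the held envelope. Section 7.6.3 expects the laptops to be used for other clients' surveys while one is outstanding, and section 2.7 plans steady monthly recruitment. The staff concerned see the other assignments: they open the envelopes, and under section 13.2 the site's Access database lists ID and arm. The block scheme is printed in a manual that section 1.2 places at every site. Once enough of the block is open, the held arm follows by subtraction.

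The same staff then decide how actively to bring the client back. In the under-half branch they schedule a return if they can and check contact details for reminder calls, with no set number of calls. In the half-or-more branch, calls throughout the two weeks are instructed.

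If effort depends on the deduced arm, entry to the trial depends on the arm. A client who lapses was never randomised and so lies outside the intent-to-treat set. The by-arm attrition test, Lee bounds and multiple imputation in section 13.4.4 do not reach such clients. Adjusting for the baseline value of the outcome cannot fully repair arm-dependent entry.

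**Working it through.** The plan gives no figure for predictability, so there is none to reproduce.

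**Inputs**
- Block size 6, 1:1, one list per site (section 8; the natural reading of its wording).
- Hold of up to 14 days (section 7.6.2).
- Site targets of 10 in the first month, then 20 to 30 per month (section 2.7), with a month of 30 days (section 3.1.4).
- Assumptions: one held slot, equally likely to be at any position in its block; staff know every other assignment at the site; further enrolments arrive at random (Poisson).

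**Step 1: certainty given k opened.** The held arm is certain when all three envelopes of the opposite arm are among the k opened out of the other five:

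P(k) = C(2, k−3) / C(5, k) for k ≥ 3, and 0 otherwise.

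So P(0) = P(1) = P(2) = 0, P(3) = 1/10, P(4) = 2/5 and P(5) = 1.

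**Step 2: average over position.** For a slot at position j with m further enrolments, k = min(5, j − 1 + m). Averaging over j = 1 to 6:
- m = 0: (0.1 + 0.4 + 1)/6 = 25%
- m = 1: (0.1 + 0.4 + 2)/6 = 42%
- m = 2: (0.1 + 0.4 + 3)/6 = 58%
- m = 3: (0.1 + 0.4 + 4)/6 = 75%
- m = 4: (0.4 + 5)/6 = 90%
- m = 5 or more: 100%

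The m = 0 value is what fixed blocks of six give with no hold.

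**Step 3: apply the recruitment targets.** The mean number of further enrolments is the monthly target × days/30. At 10 per month over 14 days the mean is 4.67, and the Poisson weights for m = 0, 1, 2, 3, 4 and 5+ are 0.009, 0.044, 0.102, 0.159, 0.186 and 0.499. Weighting the step 2 values gives 0.866.

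| Target per month | Mean in 14 days | Certain by day 7 | Certain by day 14 |
|---|---|---|---|
| 10 | 4.7 | 62% | 87% |
| 20 | 9.3 | 87% | 99% |
| 25 | 11.7 | 93% | 99.8% |
| 30 | 14.0 | 96% | about 100% |

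**Step 4: the other reading.** If the wording meant six large blocks, each would hold about 299/6 ≈ 50 of a site's IDs (101 to 399 is 299 numbers). Certainty would then be about 4% with no hold, and 13% (10 per month) to 32% (30 per month) by day 14.

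**The case against.** The plan works to prevent this situation. Section 4.2 says not to consent or enrol a client who lacks time. Section 7.6.1 asks for a verbal commitment and says to begin only with someone who can finish. Anyone at about half or more is randomised before leaving. All of that stands: the case should be uncommon, and the documents give no count.

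Timing matters too. Scheduling and checking contacts happen as the client leaves, when certainty is at the ordinary 25%. The high figures apply to later calls and to the end of the window.

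A reader might infer that selective pursuit would leave no trace. The documents do not support that. Section 7.6.2 requires an Access note and notification, section 4.1 asks for all contact attempts to be recorded, section 7.6.3 requires an email about each incomplete survey, and UCSF holds the list by ID. Destroying the paper does not destroy the allocation record, although it removes evidence that the envelope stayed sealed. UCSF could count lapses by arm; no planned analysis does so.

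A reader might also infer that varying the block size would make no difference. Varied blocks would make certain deduction much less frequent, though a best guess could still often be right. Comparing certainty under one scheme with best-guess accuracy under another would mislead.

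Finally, any bias may be small. As pure illustration, suppose that a fraction f of one arm's clients is lost selectively and differs by 0.75 HbA1c points, about half the mean adjusted SD in section 13.4.1: (1.376 + 1.634)/2 = 1.505. The shift is f × 0.75. At an assumed f of 2 to 10% that is 0.015 to 0.075, against the planned 0.4. Nothing in the documents fixes f or the 0.75.

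**Conclusion.** The concern holds as a gap in allocation concealment. The rule in section 7.6.2 undermines section 8's assurance for the clients it covers, and no other section closes the gap. On blocks of six, the hold raises the chance that the arm is known with certainty from 25% to about 87% by day 14 at 10 enrolments per month, and to 99% or more at 20 to 30. This rests on the block-size reading, Poisson arrivals at the planned rates, and staff being able to see the site's other assignments. That later envelopes are opened during a hold is inferred from sequential IDs, the targets and section 7.6.3; no section states it outright.

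Two stronger conclusions should not be drawn. Not every held envelope is deducible: at 10 per month about 13% are still not certain at day 14. And the documents show opportunity, not that staff acted on it. The number of affected clients and the resulting bias cannot be sized from them. This is worth correcting because correction is cheap, and it is not evidence that the primary comparison is biased.

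**What to change.** Separate the randomisation number from the participant ID. Keep the ID for Access and CASIC, and give the envelopes a per-site sequence number.

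Section 8 wants the envelope in plain sight throughout enrolment, because clients may otherwise suspect that it was chosen for them. That can stay: display the next unopened envelope, but bind it to the client only when it is opened at randomisation (survey finished, or the half-or-more rule met), and record its number in Access then. A client who leaves earlier holds no slot. The envelope remains next in sequence, and on return the client takes whichever is then next. An under-half survey has to be restarted anyway, so no survey data depend on the hold.

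Replace on-site destruction with return of any unused sealed envelope to UCSF. Have UCSF tabulate by allocated arm any IDs already retired under the current rule.

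The cost is relabelled envelopes, one Access field, and edits to sections 7.6.2, 8 and 12.3.2. Staff record two numbers instead of one and must keep the envelopes in sequence. The change returns predictability to the ordinary level for fixed blocks of six, about 25%; it does not remove it.

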7.6.3 CASIC instructions for completing surveys at a later date

When exiting and resuming an incomplete survey perform the following:

CASIC Online:

1. Simply exit survey using upper right hand corner exit button on pop-up survey window
2. Email [name] to let her know of incomplete assessment and plans to complete or destroy
3. When resuming, click “Start assessment” and enter PPT ID as usual
4. You will be prompted to resume baseline survey, select this option
5. Complete survey as usual

CASIC Remote:

When managing an incomplete survey on CASIC Remote, the RA can select either option outlined below.

CASIC Remote surveys that are incomplete and uploaded to the server using the “upload data” button in the “synchronize subject data” tab cannot be resumed using CASIC Remote. They can only be resumed using CASIC Online, as the data no longer “lives” on the local drive after synchronization. You may resume a survey on CASIC Remote using the instructions below only if the survey data is not synchronized after exiting the survey. However, it is best practice to synchronize the subject data, incomplete and otherwise, at the end of each day. It is likely that these computers will be used for other survey administration during the timeframe that the incomplete survey remains outstanding. It is not possible to leave only the incomplete survey on the local drive and upload the other completed surveys, and it poses a risk of lost study data if surveys are not uploaded to the server in a timely manner, so it is best to upload the incomplete survey and resume using CASIC Online.

This may be less convenient for on-site administration, but since the RA will be working with the participant to re-schedule a time, they should take into account that they will need internet access to resume the survey. For this reason, it may be useful to complete the surveys by phone. In situations in which there are no other surveys on CASIC Remote on the computer in question and there is a reasonably short time period between first administration and completion of the incomplete survey, it may be appropriate to leave the study data from the incomplete survey on the local drive and resume and complete the survey using CASIC Remote.

Option 1: Synchronize subject data and resume survey using CASIC Online:

1. Simply exit survey using upper right hand corner exit button on pop-up survey window
2. Email [name] to let her know of incomplete assessment and plans to complete or destroy

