9.1 Scope/Schema

This section outlines all in-person visits study participants have with the study staff. All dates listed below are relative to the day of enrollment for each participant (**see Appendix E**).

Participants – Intervention Group

- Day 1 (Month 1, Week 1) = T0 (by convention we identify the baseline visit as “T0”)
 - Food bank client participates in diabetes screening (blood glucose and/or HbA1c testing) event at food pantry; study staff verifies that client meets eligibility requirements for study inclusion
 - Client agrees to participate in study and completes written consent form with study staff
 - Participant completes baseline survey with study staff (CASIC)
 - Participant randomly assigned to study intervention group by study staff

- Participant receives 1st bi-monthly food box and passive education materials and receives information from food bank staff on group diabetes education classes
- Month 1, Week 2
 - Participant receives bi-monthly food box, passive education materials, and 1-on-1 education from food bank staff
 - Participant attends Session 1 of group diabetes education class around this time
- Month 2, Week 1
 - Participant receives bi-monthly food box, passive education materials, and 1-on-1 education from food bank staff
 - Participant attends Session 2 of group diabetes education class around this time
- Month 2, Week 2
 - Participant receives bi-monthly food box, passive education materials, and 1-on-1 education from food bank staff
- Month 3, Week 1
 - Participant receives bi-monthly food box, passive education materials, and 1-on-1 education from food bank staff
 - Participant attends monthly group drop-in diabetes education class around this time
- Month 3, Week 2 = T3
 - Participant completes 3-month HbA1c test with study staff
 - Participant receives bi-monthly food box, passive education materials, and 1-on-1 education from food bank staff
- Month 4, Week 1
 - Participant receives bi-monthly food box, passive education materials, and 1-on-1 education from food bank staff
 - Participant attends monthly group drop-in diabetes education class around this time
- Month 4, Week 2
 - Participant receives bi-monthly food box, passive education materials, and 1-on-1 education from food bank staff
- Month 5, Week 1
 - Participant receives bi-monthly food box, passive education materials, and 1-on-1 education from food bank staff
 - Participant attends monthly group drop-in diabetes education class around this time

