 - Participant receives bi-monthly food box, passive education materials, and 1-on-1 education from food bank staff
 - Participant completes HbA1c test with study staff
- Month 10, Week 1
 - Participant receives bi-monthly food box, passive education materials, and 1-on-1 education from food bank staff
- Month 10, Week 2

- Participant receives bi-monthly food box, passive education materials, and 1-on-1 education from food bank staff
- Month 11, Week 1
 - Participant receives bi-monthly food box, passive education materials, and 1-on-1 education from food bank staff
- Month 11, Week 2
 - Participant receives bi-monthly food box, passive education materials, and 1-on-1 education from food bank staff
- Month 12, Week 1 = T12
 - Participant receives final bi-monthly food box, passive education materials, and 1-on-1 education
 - Participant completes T12 HbA1c test with study staff
 - Participant completes T12 CONT survey with study staff (CASIC)
 - Participant receives \$15 gift card for completion of survey
 - Participant formally exits research study

9.2 *Language capacity*

Informed consent, survey administration, and diabetes education must be provided to all Spanish-speaking participants by bilingual study staff. Other study contact may be conducted with an interpreter.

9.3 *Compensation*

In order to realistically compensate participants for the time they spend participating in this research study and encourage full participation, participants will be reimbursed according to the following schedule:

- Intervention Group: \$30 gift card on completion of T6 follow-up survey; \$15 gift card on completion of T12 follow-up survey
- Wait-List Control Group: \$15 gift card on completion of baseline survey; \$15 gift card on completion of T6 follow-up survey; \$15 gift card on completion of T12 follow-up survey

Compensation will be provided in the form of assorted store gift cards (e.g., Walmart, Target, etc., but **should not include major grocery stores**). Study staff will have participants sign the “Participant Compensation Receipt Form” (**Appendix AL**) upon receipt of a gift card.

9.3.1 *Transportation Vouchers*

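### Section 7.6.2 opens the randomisation envelope on an unfinished baseline survey, contrary to sections 6 and 8 and deviation code 7, so some secondary-outcome covariates may be post-allocation

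*Combined protocol and SAP*

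**What the plan says.** Section 7.6.2 splits clients who leave early into two groups.

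- **Less than about half done.** The instruction is "Do NOT open the randomization envelope; do NOT assign client to a study group". Staff rebook within two weeks and are told: "Remind client of the program benefits / incentive available once survey is completed". If the client does not come back, the ID is retired and the envelope destroyed.
- **About half or more done.** The instruction is "If completing a baseline survey, open the randomization envelope with the participant for group assignment before the participant leaves the site". For the intervention arm it continues: "If randomized to the intervention group, provide participant with resources and first food package per study protocols". Controls receive their $15 card at the same point. The rest of the survey is to be finished within two weeks, in person or by phone. Failing that: "If, after two weeks the survey has not been completed, enter a note in ACCESS that the survey was" incomplete, and the coordinating staff are notified.

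On resuming, section 7.6.3 says: "You will be prompted to resume baseline survey, select this option". The session continues under the same participant ID, and no instruction asks for later answers to be marked.

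Section 13.4.4 analyses every outcome by ANCOVA with that outcome's own baseline value as covariate. Section 13.4.2 names two main data sources, point-of-care HbA1c and the participant survey. Section 13.4.3 lists eight secondary outcomes.

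**The concern.** The second branch reverses the order of survey and allocation that the rest of the manual relies on. The trial is unblinded, so once the envelope is open both interviewer and client know the arm. Remaining items recorded as baseline may then be coloured by that knowledge and, in the intervention arm, by the first food package. If such answers already lean towards benefit, adjusting for them removes part of the effect; if they lean the other way, it adds to it.

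There is also a practical problem. Staff who obey 7.6.2 commit a deviation that Appendix F lists by code. Section 11 requires deviations to be reported within 48 hours and warns that repeated problems can cost a site its funding.

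Finally, paying the control card before completion removes the inducement that the other branch uses to bring clients back. When the survey is never finished, the analysis plan does not say what happens to the missing covariate.

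**Working it through.** **1. Passages side by side.** The act in question is opening the envelope with the baseline survey unfinished.

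- Section 6: the survey is to precede knowledge of the allocation in every case. Direct conflict.
- Section 8: no staff member knows the arm until HbA1c, consent and the survey are all complete, and the envelope is opened after the survey. Direct conflict.
- Appendix F, code 7: randomising before the baseline survey is completed is a listed deviation. Direct conflict.
- Section 4.2: survey is step 3 and randomisation step 4; a client without enough time is not to be enrolled that day. Conflict in order, though the surrounding language is softer.
- Section 9.3: the control arm's "gift card on completion of baseline survey". Conflict for the control card only; 9.3 says nothing about food packages.

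None of these mentions the 7.6.2 case.

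**2. Which analyses it reaches.** Baseline HbA1c is taken at screening, before consent and the envelope, so the primary covariate is clean. Survey-based secondary outcomes can be affected if their items fall in the part answered late. Appendix U is not reproduced, so the number affected could be anything from 0 to 8 of the eight.

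**3. Illustrative size.** The plan gives no figure on this point and no frequency of split surveys. Inputs:

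- 300 per arm, from section 13.4.1. This reproduces: (1.960 + 1.282)² × (1.376² + 1.634²) / 0.4² = 299.8, rounded up to 300.
- Baseline slope 0.51, borrowed from the plan's HbA1c correlation (assumed for other outcomes; range 0.3-0.7).
- f, the share answering late: 2-10% (assumed), or 7-36 of 360 per arm.
- d, the shift in intervention-arm answers: 0.2-0.5 SD (assumed).

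The ANCOVA effect is the follow-up difference minus slope × baseline difference. A mean baseline shift of f × d in one arm therefore moves it by about slope × f × d. The standard error is √(2/300) × √(1 − slope²), which at 0.51 is 0.0816 × 0.860 = 0.070 SD.

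- f = 2%, d = 0.2: 0.51 × 0.02 × 0.2 = 0.0020 SD, 3% of the standard error.
- f = 5%, d = 0.2: 0.0051 SD, 7%.
- f = 5%, d = 0.5: 0.0128 SD, 18%.
- f = 10%, d = 0.5: 0.0255 SD, 36%.

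Across slopes: 0.0012-0.015 SD at 0.3 (standard error 0.0779) and 0.0028-0.035 SD at 0.7 (standard error 0.0583, so at most 0.035/0.0583 = 60%). A simulation of 4,000 trials agrees: mean bias −0.013 at f = 5%, d = 0.5; −0.024 at f = 10%, d = 0.5; and −0.034 for the latter with slope 0.7.

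**4. Baseline never obtained.** If 2-10% never finish and are dropped, n falls from 600 to 588-540. The standard error rises by √(600/588) − 1 = 1.0% to √(600/540) − 1 = 5.4%. The multiple imputation in 13.4.4 is for missing outcomes, not missing baselines.

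**The case against.** The best defence is that 7.6.2 is a deliberate exception that nobody cross-referenced. Section 4.2 speaks of every effort rather than a rule and lets the coordinating staff work out alternative enrolment and survey arrangements. Section 4.1 asks for a single visit where possible, and section 12.3.2 allows 14 days for survey entry. The exception also has a purpose: these clients have consented and have a baseline HbA1c, and randomising them at once keeps them for the primary outcome. This shows that split surveys were foreseen. It does not show that opening the envelope early was allowed, because sections 6 and 8 leave no room for it and code 7 names it as a deviation.

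Several limiting points stand.

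- The path should be uncommon: section 7.6.1 says to start only with someone who commits to finishing.
- Affected people can be found. Section 7.6.3 requires an email about each incomplete assessment, 7.6.2 a note when a survey is never finished, and the deviation log carries ID and date.
- The top of the assumed range is harsh. A 0.5 SD shift within two weeks is about twice the six-month HbA1c effect the trial is powered for (0.4/1.76 = 0.23 SD; a different outcome, so only a scale check).
- Differential completion by arm is not established, since reminder calls and phone completion apply to both arms.

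A reader might also infer that late baseline answers follow the second food box and a class, because section 9.1 says for Month 1, Week 2: "Participant attends Session 1 of group diabetes education class around this time". The documents do not support that firmly. Section 3.4.1 allows a month for session 1, and the week labels mark the two distributions in each month, so the second box may fall at or after the end of the two-week window. Only the first package clearly comes before late answers.

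**Conclusion.** The contradiction is certain and does not depend on how often the path is used. Its statistical consequence is minor: post-allocation answers can enter as baseline covariates for some survey-based secondary outcomes, and a baseline never obtained has no stated handling. On plausible assumed values the bias is a few per cent of a standard error. It reaches about a third only at the top of the assumed range with slope 0.51, and more only if the slope is also at its upper end. These sizes rest on assumed f, d and slope, and which outcomes are exposed is unknown.

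Two stronger inferences are not supported. Concealment before enrolment is not broken and the primary HbA1c comparison is not biased, since consent and HbA1c precede the envelope on this path too. Nor can it be said that any particular secondary outcome is contaminated, because the item order is not shown.

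**What to change.** **Section 7.6.2.** Apply the envelope rule of the less-than-half branch to every unfinished baseline survey. Saving and resuming stay allowed, but the envelope stays sealed, and nothing that depends on the arm is given, until the survey is completed within the existing two-week window. If an envelope is opened early, log code 7 and flag the items answered afterwards.

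**Section 13.4.4.** Treat baseline items answered after opening, or never answered, as missing, by one rule applied identically in both arms. A pooled mean plus missing indicator is one option.

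Stating the exception in every section and adding a sensitivity analysis would also remove the contradiction. It would leave post-allocation covariates in the main secondary analyses.

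**Cost.** Wording, and a few consented clients with a baseline HbA1c who do not return and are not randomised. If 2-10% of a site's 240 recruits leave part-way (5-24) and half do not return (both assumed), 2-12 need replacing. Each site has 299 IDs (for example 399 − 101 + 1), so 299 − 240 = 59 are spare, or 299 − 260 = 39 on the section 2.7 timeline, less any already retired. Retired IDs leave some blocks of six incomplete, as the less-than-half rule already does.
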